3.2 SECONDARY OBJECTIVES AND ENDPOINTS

Secondary objective 1:

To determine the effect of the different prime/boost regimens on the magnitude and polyfunctionality of T-cell responses induced by the different priming vaccinations

Secondary endpoint 1:

Rate, magnitude and polyfunctionality of CD4⁺ and CD8⁺ T-cell responses measured by ICS to p24CE and HIV Gag, 2 weeks after the second and fourth vaccinations

Secondary objective 2:

To determine the effect of the different prime/boost regimens on the specificity of T-cell responses induced by the different primes

Secondary endpoint 2:

Epitope specificity of T-cell responses measured by IFN- γ ELISpot to p24CE and HIV Gag, 2 weeks after the second and fourth vaccinations

Secondary objective 3:

To evaluate the humoral immunogenicity of the HIV-1 pDNA vaccines p24CE1/2 and p55^{gag} administered alone, in combination, or sequentially by intramuscular injection with electroporation

Secondary endpoint 3:

Rate and magnitude of humoral immune responses to Gag measured 2 weeks after the 4th vaccination by binding antibody multiplex assay

Secondary objective 4:

To determine the frequency of circulating Tfh in response to each vaccination regimen

Secondary endpoint 4:

Rate and magnitude of CD4⁺ cTfh measured by ICS

3.3 EXPLORATORY OBJECTIVES

Exploratory objective 1:

To further evaluate immunogenicity of the different vaccine regimens, additional immunogenicity assays may be performed, including on samples from other time points, based on the HVTN Laboratory Assay Algorithm

Exploratory objective 2:

To determine the frequency of plasmablasts in response to each vaccination regimen

Exploratory objective 3:

To evaluate the breadth of the T cell receptor repertoire induced after pDNA vaccination by electroporation

Exploratory objective 4:

To conduct analyses related to furthering the understanding of HIV, immunology, vaccines, and clinical trial conduct

4. COHORT DEFINITION

Recruitment will target enrolling 56 healthy, HIV-uninfected adult participants, aged 18 to 50 years.

To ensure that both men and women will be adequately represented in the trial, the trial will enroll at least approximately 40% of each sex overall. Hence, when approximately 33 participants of one sex are enrolled, recruitment of persons born of that sex will stop.

Since enrollment is concurrent with receiving the first study vaccination, all enrolled participants will provide some safety data. However, for immunogenicity analyses, it is possible that data may be missing for various reasons, such as participants terminating from the study early, problems in shipping specimens, low cell viability of processed peripheral blood mononuclear cells (PBMCs) or high background.

At the enrollment visit, if a participant had the Ichor TDS-IM EP device applied to the participant's arm but the participant was not able to receive any injection of study product, the participant is not considered enrolled into the study, and is referred to as a "device-only participant". Unenrolled, device-only participants will also provide some safety data.

5. POTENTIAL CONFOUNDERS

Characterization of the safety of the vaccine is susceptible to confounding by adverse events not related to the vaccine that by chance occur more often in one arm of the trial than another. Therefore analyses involving adverse events will incorporate the reported relationship to product as assessed by HVTN staff.

6. RANDOMIZATION

The randomization sequence was obtained by computer-generated random numbers and provided to each HVTN CRS through a Web-based randomization system. The randomization was done in blocks to ensure balance across arms. At each institution, the pharmacist with primary responsibility for dispensing study products is charged with maintaining security of the treatment assignments (except in emergency situations as specified in the HVTN MOP).

7. BLINDING

Participants and site staff (except for site pharmacists) will be blinded as to participant treatment arm assignments (i.e., blinded to both group and vaccine/control status). Study product assignments are accessible to those HVTN CRS pharmacists, DAIDS protocol pharmacists and contract monitors, and SDMC staff who are required to know this information in order to ensure proper trial conduct. Any discussion of study product assignment between pharmacy staff and any other HVTN CRS staff is prohibited. The HVTN SMB members also are unblinded to treatment assignment in order to conduct review of trial safety.

When a participant leaves the trial prior to study completion, the participant will be told he or she must wait until all participants are unblinded to learn his or her treatment assignment.

Emergency unblinding decisions will be made by the site investigator. If time permits, the HVTN PSRT should be consulted before emergency unblinding occurs.

8. STATISTICAL ANALYSIS

All data from enrolled participants will be analyzed according to the initial randomization assignment regardless of how many vaccinations they received. In the rare instance that a participant receives the wrong treatment at a specific vaccination time, the Statistical Analysis Plan will address how to analyze the participant's safety data. Analyses are modified intent-to-treat in that individuals who are randomized but not enrolled do not contribute data and hence are excluded. Because of blinding and the brief length of time between randomization and enrollment—typically no more than 4 working days—very few such individuals are expected.

Analyses for primary endpoints will be performed using SAS and R. All other descriptive and inferential statistical analyses will be performed using SAS, StatXact, or R statistical software.

No formal multiple comparison adjustments will be employed for multiple safety endpoints, multiple primary immunogenicity endpoints, or secondary endpoints. However, multiplicity adjustments will be made for certain immunogenicity assays, as discussed below, when the assay endpoint is viewed as a collection of hypotheses (e.g., testing multiple peptide pools to determine a positive response).

8.1 ANALYSIS VARIABLES

The analysis variables consist of baseline participant characteristics, safety, and immunogenicity for primary- and secondary-objective analyses.

8.2 BASELINE COMPARABILITY

Treatment arms will be compared for baseline participant characteristics using descriptive statistics.

8.3 SAFETY/TOLERABILITY ANALYSIS

Since enrollment is concurrent with receiving the first vaccination, all participants will have received at least 1 vaccination and therefore will provide some safety data.

8.3.1 REACTOGENICITY

The number and percentage of participants experiencing each type of reactogenicity sign or symptom will be tabulated by severity and treatment arm and the percentages displayed graphically by arm. For a given sign or symptom, each participant's reactogenicity will be counted once under the maximum severity for all injection visits. In addition, to the individual types of events, the maximum severity of local pain or tenderness, induration or erythema, and of systemic symptoms will be calculated. Kruskal-Wallis tests will be used to test for differences in severity between arms.

8.3.2 AEs, SAEs, and AESIs

AEs will be summarized using MedDRA System Organ Class and preferred terms. Tables will show by treatment arm the number and percentage of participants experiencing an AE within a System Organ Class or within preferred term category by severity or by relationship to study product. For the calculations in these tables, a participant with multiple AEs within a category will be counted

once under the maximum severity or the strongest recorded causal relationship to study product. Formal statistical testing comparing arms is not planned since interpretation of differences must rely heavily upon clinical judgment.

A listing of SAEs reported to the DAIDS Regulatory Support Center (RSC) Safety Office will provide details of the events including severity, relationship to study product, time between onset and last vaccination, and number of vaccinations received. A separate listing will do the same for AEs of special interest (AESI). AESI for this protocol include but are not limited to autoimmune disorders; a sample list of AESI is provided in Appendix G.

8.3.3 LOCAL LABORATORY VALUES

Box plots of local laboratory values will be generated for baseline values and for values measured during the course of the study by treatment arm and visit. Each box plot will show the first quartile, the median, and the third quartile. Outliers (values outside the box plot) will also be plotted. If appropriate, horizontal lines representing boundaries for abnormal values will be plotted.

For each local laboratory measure, summary statistics will be presented by treatment arm and time point, as well as changes from baseline for post-enrollment values. In addition, the number (percentage) of participants with local laboratory values recorded as meeting Grade 1 AE criteria or above as specified in the Division of AIDS Table for Grading the Severity of Adult and Pediatric Adverse Events will be tabulated by treatment arm for each post-vaccination time point. Reportable clinical laboratory abnormalities without an associated clinical diagnosis will also be included in the tabulation of AEs described above.

8.3.4 REASONS FOR VACCINATION DISCONTINUATION AND EARLY STUDY TERMINATION

The number and percentage of participants who discontinue vaccination and who terminate the study early will be tabulated by reason and treatment arm.

8.4 IMMUNOGENICITY ANALYSIS

8.4.1 GENERAL APPROACH

For the statistical analysis of immunogenicity endpoints, data from enrolled participants will be used according to the initial randomization assignment regardless of how many injections they received. Additional analyses may be performed, limited to participants who received all scheduled injections per protocol. Assay results that are unreliable, from specimens collected outside of the visit window, or from HIV-infected participants post-infection are excluded. Since the exact date of HIV infection is unknown, any assay data from blood draws 4 weeks prior to an infected participant's last seronegative sample and thereafter may be excluded. If an HIV-infected participant does not have a seronegative sample post-enrollment, then all data from that participant may be excluded from the analysis.

Discrete categorical assay endpoints (e.g., response rates) will be analyzed by tabulating the frequency of positive response for each assay by antigen and

treatment arm at each timepoint for which an assessment is performed. Crude response rates will be presented with their corresponding 95% confidence interval estimates calculated using the score test method [1]. Because of the small numbers of control participants in each group, no adjustment will be made to the vaccine arm estimates for the false positive rates in the control arms. Fisher's exact tests will be used to compare the response rates of any 2 vaccine arms, with a significant difference declared if the 2-sided p-value is ≤ 0.05 .

For quantitative assay data (e.g., percentage of positive cells from the ICS assay or mean fluorescence intensity from the binding antibody multiplex assay), graphical and tabular summaries of the distributions by antigen, treatment arm, and timepoint will be made. For all primary and secondary immunogenicity endpoints, box plots and plots of estimated reverse cumulative distribution curves will be used for graphical display of all of the study arms. Typically, the results will be shown for each vaccine arm and for the set of control arms pooled into one group.

The differences between treatment groups at 2 weeks post the 2nd and 4th vaccination timepoints will be tested with a nonparametric Wilcoxon rank sum test if the data are not normally distributed and with a 2-sample t-test if the data appear to be normally distributed.

Some immunologic assays have underlying continuous or count-type readouts that are dichotomized into responder/non-responder categories (e.g., ICS and BAMA). If treatment arm differences for these assays are best summarized by a mixture model, then Lachenbruch's test statistic [2] will be used to evaluate the composite null hypothesis of equal response rates in the 2 arms and equal response distributions among responders in the 2 such arms. This test statistic equals the square of a binomial Z-statistic for comparing the response rates plus the square of a Wilcoxon statistic for comparing the response distributions in the subgroup of responders. A permutation procedure is used to obtain a 2-sided p-value. For estimation, differences in response rates between arms will be estimated using the methods described above, and in the subgroup of positive responders, differences in location parameters between arms will be estimated using the methods described above.

More sophisticated analyses employing repeated measures methodology (e.g., linear mixed models or marginal mean models fit by generalized estimating equations) may be utilized to incorporate immune responses over several timepoints and to test for differences over time. However, inference from such analyses would be limited by the small sample size of this study. All statistical tests will be 2-sided and will be considered statistically significant if $p \leq 0.05$.

Based upon previous HVTN trials, missing 17% of immunogenicity results for a specific assay is common due to study participants terminating from the study early, problems in shipping specimens, or low cell viability of processed peripheral blood mononuclear cells (PBMCs). To achieve unbiased statistical estimation and inferences with standard methods applied in a complete-case manner (only including participants with observed data in the analysis), missing data need to be missing completely at random (MCAR). Following the most commonly used definition, MCAR assumes that the probability of an observation being missing does not depend on any participant characteristics (observed or unobserved). When missing data are minimal (specifically if no more than 20% of

participants are missing any values), then standard complete-case methods will be used, because violations of the MCAR assumption will have little impact on the estimates and hypothesis tests.

If a substantial amount of immunogenicity data is missing for an endpoint (at least 1 value missing from more than 20% of participants), then using the methods that require the MCAR assumption may give misleading results. In this situation, analyses of the immunogenicity endpoints at a specific timepoint will be performed using parametric generalized linear models fit by maximum likelihood. These methods provide unbiased estimation and inferences under the parametric modeling assumptions and the assumption that the missing data are missing at random (MAR). MAR assumes that the probability of an observation being missing may depend upon the observed responses and upon observed covariates, but not upon any unobserved factors. Generalized linear models for response rates will use a binomial error distribution and for quantitative endpoints, a normal error distribution. For assessing repeated immunogenicity measurement, linear mixed effects models will be used. If the immunological outcomes are left- and/or right- censored, then the linear mixed effects models of Hughes [3] will be used, because they accommodate the censoring. In addition, secondary analyses of repeated immunogenicity measurements may be done using weighted GEE [4] methods, which are valid under MAR. All of the models described above in this paragraph will include as covariates all available baseline predictors of the missing outcomes.

8.4.2 ANALYSIS OF CD4+ AND CD8+ T-CELL RESPONSE AS MEASURED BY THE ICS ASSAY

The analysis of CD4⁺ and CD8⁺ T-cell response rates as measured by the ICS assay will be evaluated and compared as described under the general approach. For each T-cell subset, the positivity call for each peptide pool will include a multiple comparison adjustment for the number of peptide pools used in the assay. In general, the Mixture Models for Single-cell Assays (MIMOSA) statistical framework [5] and/or the Fisher's exact test-based positivity criteria will be used. The magnitude of marginal response will be analyzed as described for quantitative data in the general approach section. For each T-cell subset, graphs will be used to display the background-subtracted magnitudes for each participant by protein, treatment arm and timepoint. Statistical testing comparing the magnitudes will be based on positive responders only. The polyfunctionality of ICS responses will also be analyzed as a secondary endpoint. Besides descriptive plots of the magnitude of polyfunctional responses, the COMPASS (Combinatorial Polyfunctionality analysis of Antigen-Specific T-cell Subsets) statistical framework [6] will also be used to perform joint modelling of multiple T-cell subsets of different cytokine combinations using the functionality score (FS) and the polyfunctionality score (PFS) to summarize the multi-parameter ICS responses.

8.4.3 ANALYSIS OF MULTIPLEXED IMMUNOASSAY DATA

The analysis of response rates and response magnitudes will be evaluated and compared as described under the general approach.

8.5 ANALYSIS PRIOR TO END OF SCHEDULED FOLLOW-UP VISITS

Any analyses conducted prior to the end of the scheduled follow-up visits should not compromise the integrity of the trial in terms of participant retention or safety or immunogenicity endpoint assessments. In particular, early unblinded analyses by treatment assignment require careful consideration and should be made available on a need to know basis only.

8.5.1 SAFETY

During the course of the trial, unblinded analyses of safety data will be prepared approximately every 4 months during the main study for review by the SMB. Ad hoc safety reports may also be prepared for SMB review at the request of the HVTN PSRT. The HVTN leadership must approve any other requests for unblinded safety data prior to the end of the scheduled follow-up visits.

8.5.2 IMMUNOGENICITY

An unblinded statistical analysis by treatment assignment of a primary immunogenicity endpoint may be performed when all participants have completed the corresponding primary immunogenicity visit and data are available for analysis from at least 80% of these participants. Similarly, an unblinded statistical analysis by treatment assignment of a secondary or exploratory immunogenicity endpoint may be performed when all participants have completed the corresponding immunogenicity visit and data are available for analysis from at least 80% of these participants. However, such analyses for a secondary or exploratory immunogenicity endpoint will only take place after at least one of the primary immunogenicity endpoints of the same class (humoral or cell-mediated) or, if no primary endpoint of the same class, at least one of the primary immunogenicity endpoints reaches the aforementioned threshold. The Laboratory Program will review the analysis report prior to distribution to the protocol chairs, DAIDS, vaccine developer, and other key HVTN members and investigators. Distribution of reports will be limited to those with a need to know for the purpose of informing future trial-related decisions. The HVTN leadership must approve any other requests for HVTN immunogenicity analyses prior to the end of the scheduled follow-up visits.

9. SAFETY TABLES AND FIGURES

9.1 LIST OF SMB TABLES

- Enrollment Report
- Demographics and Study Product Administration Frequencies
- Overall Protocol Status
- Discontinuation Status Listing
- Study Product Administration Errors Listing
- Maximum Local Reactogenicity Summary
- Maximum Systemic Reactogenicity Summary
- Severe or Life-Threatening Local Reactogenicities Listing

- Severe or Life-Threatening Systemic Reactogenicities Listing
- Moderate, Severe, or Life-Threatening Erythema/Induration Listing
- AEs by Body System and Severity
- AEs by Preferred Term and Severity – Includes Severe, Life-Threatening, or Fatal Events Only
- AEs by Preferred Term and Severity – Includes All Severities
- AEs by Preferred Term and Severity – Includes Related Events Only
- AEs by Preferred Term and Severity – Includes Events Related to the EP Device Only
- AEs by Preferred Term and Relationship to Study Product – Includes Events of Any Relationship
- Severe, Life-Threatening, or Fatal Adverse Events Listing
- Adverse Events of Special Interest Listing
- Related Adverse Events Listing
- Device Related Adverse Events Listing
- EAEs Reported to the RSC Listing
- Pregnancy Listing
- HIV Infection Listing
- Listing of Device-Only Participants
- Listing of Device-Only Participant AEs

9.2 LIST OF SMB FIGURES

- Maximum Local Reactogenicities
- Maximum Systemic Reactogenicities
- Boxplots for platelets, WBC, lymphocytes, neutrophils, hemoglobin, alkaline phosphate, AST, ALT, and creatinine at baseline and each post-vaccination follow-up visit

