11.1.2 HVTN SMB

The SMB is a multidisciplinary group consisting of biostatisticians, clinicians, and experts in HIV vaccine research that, collectively, has experience in the conduct and monitoring of vaccine trials. Members of the SMB are not directly affiliated with the protocols under review.

The SMB reviews safety data, unblinded as to treatment arm, approximately every 4 months. The reviews consist of evaluation of cumulative reactogenicity events, AE, laboratory safety data, and individual reports of adverse events requiring expedited reporting to DAIDS. To increase the sensitivity for detecting potential safety problems, the SMB will review safety data aggregated across multiple protocols that use the same or similar vaccine candidates. The SMB conducts additional special reviews at the request of the HVTN 119 PSRT.

Study sites will receive SMB summary minutes and are responsible for forwarding them to their IRB/EC and any applicable RE.

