3. OBJECTIVES AND ENDPOINTS

3.1 PRIMARY OBJECTIVES AND ENDPOINTS

Primary objective 1:

To evaluate the safety and tolerability of the HIV-1 pDNA vaccines p24CE1/2 and p55^{gag} administered with IL-12 pDNA by intramuscular injection with electroporation

Primary endpoints 1:

- Frequency and severity of local injection/EP site and systemic reactogenicity signs and symptoms
- Frequency of AEs categorized by MedDRA body system, MedDRA preferred term, severity and assessed relationship to study products. Detailed description of all AEs meeting DAIDS criteria for expedited reporting
- The distribution of values of safety laboratory measures at baseline and at follow-up visits post vaccination
- Number of participants with early discontinuation of vaccinations and reason for discontinuation
- Magnitude of local injection/EP site pain as measured by a visual analog scale
- Distribution of responses to questions regarding acceptability of study injection procedures

Primary objective 2:

To compare the two pDNA prime/boost strategies with respect to breadth (defined as the number of targeted CEs) of CD4⁺ and CD8⁺ T-cell responses to conserved regions of the p24^{Gag} protein

Primary endpoint 2:

The number of targeted CEs by CD4⁺ and CD8⁺ T-cell responses measured by ICS 2 weeks after the second and fourth vaccinations

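### CPK is missing from the laboratory boxplot lists in SAP 9.2 and 9.4, so routine SMB outputs show it by arm only through reported AEs

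*SAP*

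**What the plan says.** - **What is measured.** Protocol 9.2 defines the chemistry panel as ALT, AST, alkaline phosphatase, creatinine and CPK. Protocol 9.4 and Appendix F carry the same panel into follow-up, and Appendices E and F schedule it at D14, D42, D98, D182 and D273.
- **The general rule.** SAP 8.3.3 states: "Box plots of local laboratory values will be generated for baseline values and for values measured during the course of the study". The plots are split by visit and arm, and no analyte is named as excluded. The section adds: "For each local laboratory measure, summary statistics will be presented by treatment arm and time point", with changes from baseline, and counts of values at Grade 1 or above.
- **The output lists.** The figure lists for the SMB (SAP 9.2) and the final report (SAP 9.4) carry the same line: "Boxplots for platelets, WBC, lymphocytes, neutrophils, hemoglobin, alkaline phosphate, AST, ALT, and creatinine at baseline and each post-vaccination follow-up visit". I read the alkaline phosphate entry as alkaline phosphatase. CPK is not there, and no reason is given.
- **The AE route.** SAP 8.3.3 also provides: "Reportable clinical laboratory abnormalities without an associated clinical diagnosis will also be included in the tabulation of AEs described above". SAP 8.3.2 presents the AE tables by treatment arm.
- **The endpoint.** One primary safety endpoint (SAP 3.1) is: "The distribution of values of safety laboratory measures at baseline and at follow-up visits post vaccination".
- **The SMB.** Protocol 11.1.2 says: "The SMB reviews safety data, unblinded as to treatment arm, approximately every 4 months". It lists laboratory safety data as a review item separate from AEs.

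**The concern.** The lists plot four chemistry analytes and omit the one most closely tied to the delivery method. Protocol 4.5 includes a CPK rise among events seen with the EP device, and no other panel analyte appears there. Table 4-4 lists injection-site muscle damage as a risk. Both entries are qualified: the events in 4.5 are described as transient and mild or moderate, with no serious device-related event reported, and Table 4-4 places muscle damage in its uncommon-or-rare category.

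At stake is what the SMB sees in its routine package. It is the body that reviews data unblinded by arm. Protocol 11.2.3 seeks to preserve the PSRT's blind, and under Protocol 11.5.1 the daily review by HVTN Core is blinded. If CPK values shifted in one vaccine arm without being reported as AEs, nothing in the listed SMB outputs would show it. Inclusion criterion 15 allows entry with CPK up to 2.0 times the upper limit of normal, so some participants may start above normal. A later value is then easier to interpret beside the baseline distribution.

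**Working it through.** No power or error-rate figure is involved. The check is a comparison of lists and a count of scheduled values.

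**1. Panel against plots**

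| Chemistry analyte (Protocol 9.2) | SAP 9.2 (SMB) | SAP 9.4 (final report) |
|---|---|---|
| ALT | plotted | plotted |
| AST | plotted | plotted |
| Alkaline phosphatase | plotted | plotted |
| Creatinine | plotted | plotted |
| CPK | not listed | not listed |

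Each figure list names 9 analytes: 5 haematology and 4 chemistry. Against a panel of 5, that leaves 5 − 4 = 1 unplotted, which is CPK.

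**2. Other outputs that could carry CPK values**

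- SAP 9.1 (SMB tables): 25 items, of which 0 are laboratory-value tables. CPK can enter only through the AE tables and listings, including those for device-related events.
- SAP 9.3 (final-report tables): 30 items, of which 2 are laboratory-value tables (values at Grade 1 or above, and summary statistics). Neither is restricted by analyte, so both cover CPK.

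The 9.2 boxplots are therefore the only listed SMB output that displays laboratory values as such. An analyte absent from them reaches the SMB only as a reported AE.

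**3. Values already scheduled**

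- Baseline: 56.
- After enrolment: 5 draws × 56 participants = 280, made up of 5 × 50 = 250 from vaccinees and 5 × 6 = 30 from placebo recipients.
- Per draw: 25 in each vaccine arm and 3 in each placebo arm.

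These are whole-study totals under full attendance. Missed visits would lower them, repeat laboratory tests could raise them, and any single SMB report would hold only what had accrued by then.

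**4. Timing of the draws**

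Doses are on D0, D28, D84 and D168. Nominal intervals from the latest dose are 14 − 0, 42 − 28, 98 − 84 and 182 − 168, which is 14 days each, and 273 − 168 = 105 days. Visit windows are in the Study Specific Procedures, so actual intervals may differ somewhat. A rise that resolves within two weeks may be missed.

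**The case against.** **The lists may be a deliberate selection.** SAP 8.3.3 does not promise a plot of every analyte, and of the white-cell differential only lymphocytes and neutrophils are plotted. This stands as a possible explanation. It does not supply a reason for leaving out CPK while plotting the rest of its panel.

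**The SMB already sees CPK by arm.** A reader might infer that the SMB has no by-arm view of CPK at all. The documents do not support that. AE tables are shown by arm, they include reportable laboratory abnormalities, and the SMB receives them unblinded, with separate device-related outputs. Only values not reported as AEs are missing.

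**The primary endpoint is analysed.** A reader might also infer that the laboratory endpoint goes unanalysed for CPK. It does not. SAP 8.3.3 requires summary statistics and changes from baseline for each laboratory measure, and SAP 9.3 lists the tables.

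**More can be requested.** SAP 8.5.1 says: "Ad hoc safety reports may also be prepared for SMB review at the request of the HVTN PSRT". Protocol 11.1.2 adds: "The SMB conducts additional special reviews at the request of the HVTN 119 PSRT". Both routes are real, but the request comes from a team that is meant to stay blinded and so has no by-arm CPK distribution to prompt it.

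**The SAP will be revised.** SAP section 1 provides for review and update before the final safety analysis. That could repair 9.4. It does not address 9.2, because the SMB reviews run during the main study.

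**The yield is small.** Draws are nominally at least 14 days after a dose, 6 participants receive placebo, and every arm receives EP, so a shift from baseline in all arms would not by itself isolate a device effect. This stands, and it limits the severity. The same limits apply to the four chemistry analytes that are plotted, so they are no reason to treat CPK differently.

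**Conclusion.** The point holds, is minor, and is best described as a free improvement. One of five chemistry-panel analytes, CPK, is absent from both boxplot lists, and those lists are narrower than SAP 8.3.3 read on its own. With 0 laboratory-value tables among 25 SMB items, the routine SMB package gives CPK by arm only as reported AEs. It does not show the by-arm distribution of the remaining values, or how that distribution moves from baseline. In the final report the gap is one plot.

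This rests on two assumptions: that the SMB outputs are produced as listed, with no ad hoc addition, and that the lists in SAP 9.2 and 9.4 govern where they are narrower than 8.3.3. If the general rule in 8.3.3 is taken to govern, CPK would be plotted anyway and only the lists need correcting. The documents record no decision to exclude CPK, and nothing in them shows that a safety signal would be missed.

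**What to change.** Add CPK to the boxplot lists in SAP 9.2 and 9.4, shown by treatment arm at baseline and each scheduled chemistry visit, exactly as for the other analytes. The placebo arms should not be pooled in the CPK panel alone, because that would depart from the by-arm rule in SAP 8.3.3 and from the other nine analytes. If the omission was intended, one sentence in SAP 8.3.3 should say that the lists are a selection and why CPK is not in it.

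The plot shows a shift in distribution. Within-participant change from baseline stays in the final-report tables, as for every other analyte. The change closes the gap for the chemistry panel only; the unplotted parts of the differential are a separate choice.

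The cost is one more panel in an existing figure. No new data, visits or samples are needed.
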